Aim 1: Conduct a feasibility and acceptability study of the RELAX approach in migraine and post-traumatic headache (PTH) patients who visit the NYU Department of Neurology General Practice and/or subspecialty groups or the NYU Concussion Center. We will recruit and randomize subjects (N=400) in the FGP Neurology Group including the MS Center and Headache Center and the NYU Concussion Center to receive the RELAX intervention or monitored usual care (MUC). Both groups will be asked to complete daily diaries, and data will also be collected on measures of recruitment, retention, adherence, and satisfaction with the PMR, the clinically important endpoint. With the PMR, we hypothesize that at least 70% of participants will be adherers (e.g., use RELAXaHEAD at least 4 days/week for 12 weeks). We will assess if the daily diary is acceptable by examining whether there is differential attrition with daily diary completion. We hypothesize no difference between the two groups for acceptability of the diary. We will define acceptability as an average score of ≥4 (0-5 Likert scale) on the 9-item acceptability questionnaire. The outcomes for Aim 1 are the feasibility/acceptability outcomes; number of days of diary entered, number of days of pmr, time spent/day on pmr (Please refer to Table 2)

Aim 2: Conduct within group analyses of the RELAX approach vs MUC.

In the migraine patient population, the primary outcome will be migraine quality of life and migraine disability measured by Migraine Quality of Life (MSQ) and the MIDAS. In the migraine-MS population, a primary outcome will also be MS pain related disability as measured by the MOS Pain Effects Scale (PES). ¹⁵ Secondary outcomes include headache frequency and intensity, stress levels, sleep and psychiatric screens (NIH PROMIS depression and anxiety screens). We hypothesize that at 3 months compared with baseline there will be trends in the RELAX arm towards decreased disability (as measured by the Migraine Disability Assessment Scale (MIDAS)) and improvements in MS pain related quality of life in the MS-migraine patient population.

In the PTH patient population, we will examine the secondary outcomes noted above.

Background

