Our initial sample size was justified based on the feasibility outcome of compliance with PMR among patients in the RELAX group. We anticipated an initial compliance rate of at least 75%. The planned sample size also provided adequate power for the primary exploratory outcome (\square MIDAS from baseline to 3 months) and the secondary outcome (number of headaches/30 days). Considering \square MIDAS as the primary outcome can reduce data skewedness and improve study power. Based on the study, the standard deviation (SD) of \square MIDAS ranges from 5 to 7. Using the conservative estimate of SD=7, group sample sizes of 30, with anticipated 25% dropout leading to approximately 23 patients per group, achieve 80% power to detect a clinically significant difference of 5.75 between the groups, assuming a significance level of 0.05 using a two-sided two-sample t-test.

Subsequently, based on later data, we found that only about half of the participants have full follow-through so the 90 (similar to the NIH request) is more adequate for this.

GenderofSubjects

Both genders will be included.

AgeofSubjects

18-80 (18 – 65 in urgent care)

Racialand Ethnic Origin No enrollment restrictions.

Inclusion Criteria [Box1] age 18-80;(18-65 in urgent care)

Meets migraine criteria based on International Classification of Headache Disorders (ICHD) 3 beta (based on questions in REDCap), Migraine Disability Assessment (MIDAS) score >5. 4+ headache days a month.

OR

Meets Chronic PTH criteria based on International Classification of Headache Disorders (ICHD) 3 beta (based on questions in REDCap) and had 4+ headache days a month, is 3-12 months post initial injury.

OR

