Week 5: pmr at least 3 days a week (optional body scan)

Weeks 6-8: use when it is most helpful (falling asleep, HA coming on, stress)

The study intervention will be 8 weeks in duration but the full study length will be 6 months. There will be a baseline assessment (T0), a f/u call or email at one week (T1), a 30 day phone call or email assessment (T2), a 60 day phone call/email (T3), and a 90 day phone call/email (T4) (to examine persistence of effect after a month). The last follow up will be at 6 months to examine persistence of effect 4 months after the intervention ends. As we learned previously, we are adding the option for email as some subjects prefer email.

The MUC session is where the subjects are explained that in migraine treatment, they may be given medications to take to stop a migraine and medications to prevent a migraine. The mainstay of migraine management is a headache diary where people can track their headache days, headache intensity, medications taken, and any other details they think might be pertinent to share with their medical provider. No written material is provided during this session.

MUC: To match the time spent with the designated study team member, subjects will be given a general education session consisting of basic migraine information, such as evidence-based ways to treat headaches: treat early, limit acute medications < 2–3 days/week, and call the primary care physician (PCP) if abortive medications are used more frequently. They will be shown a website: https://[name].wixsite.com/relaxahead (to be renamed). The study team member will load the app onto the subject's smartphone but the PMR component will be blocked on the version of the app that the MUC subject receives.

All subjects will be asked to track headache frequency, intensity, and acute medication use on app. All subjects will get the post enrollment card after they have been enrolled so that they have some instructions on what to do when they go home.

All subjects will receive written educational material about migraine.³⁰ All subjects will receive follow-up phone calls, texts, and/or SendSafe emails at 1 week of enrollment and 1, 2, 3, and 6 months after study enrollment. (The choice of calls, texts or emails came from prior subjects who participated in IRB approved study focus groups.) The study team has permission from MCIT to send the following text messages (and an emailing indicating such approval is part of the submission process):

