The following questionnaires: PROMIS depression and anxiety screens, Insomnia Sleep Index (ISI) and the Perceived Stress Scale will be administered via REDCap.

In addition to the application, REDCap, a HIPAA Compliant research database system will be used. The study identifier and the PHI of the subjects will be stored in REDCap. In addition, we will use REDCap to send out the MIDAS to the subjects.

We will use the REDCap randomization feature to randomize our subjects.

DataAnalysis and DataMonitoring Analysis Plan

Table 2 describes the outcome measures that will be used. We considered the feasibility outcome measures recommended by Kraemer and colleagues for pilot studies.³¹ For this study, feasibility will be operationally defined as study recruitment, retention, and adherence measures for doing the PMR. Acceptability will be operationally defined as attrition, satisfaction, and willingness to participate in a similar intervention in the future. Satisfaction questions are as follows:

Responses will be 0-5 on the Likert Scale:

Daily Diary Satisfaction Questions

- 1. The app was easy to use
- 2. The information was easy to understand
- 3. The daily diary was relevant to me to help track my headaches
- 4. The app kept my interest and attention
- 5. I would be happy to use the app again

PMR Satisfaction Questions

- 1. The relaxation kept my interest and attention
- 2. The relaxation helped to improve my stress and low mood
- 3. The relaxation taught me skills that will help me handle future problems
- 4. I would be happy to do the relaxation again

Our primary outcome will be the change in the MSQv2 -a validated migraine quality of life measure (https://eprovide.mapi-trust.org/instruments/migraine-specific-quality-of-life-questionnaire). We will also use the Migraine Disability Assessment Scale (MIDAS), measures disability over the past 3 months. 32-35 MIDAS scores have been shown to have excellent test-retest reliability, high internal consistency, and high external validity using a variety of measures—including diary-based measures. 32,34 MIDAS scores are also positively associated with physician judgements about the severity of headache and the need for treatment. 33 In the MS- migraine patient population, we will also assess the MOS Pain Effects Scale (PES).

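### Comparing attrition between two arms that both keep the diary cannot show whether the diary itself is acceptable, and the 9-item score only partly fills the gap

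*Combined protocol and SAP*

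**What the plan says.** Under Purpose of the Study, Aim 1, the diary is a task for everyone: "Both groups will be asked to complete daily diaries". The method for judging it is: "We will assess if the daily diary is acceptable by examining whether there is differential attrition with daily diary completion". The hypothesis follows: "We hypothesize no difference between the two groups for acceptability of the diary". The next sentence gives an absolute criterion: "We will define acceptability as an average score of ≥4 (0-5 Likert scale) on the 9-item acceptability questionnaire".

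The Analysis Plan gives another definition: "Acceptability will be operationally defined as attrition, satisfaction, and willingness to participate in a similar intervention in the future". It lists the nine satisfaction items, five on the diary and app and four on relaxation. Table 2 names attrition as an acceptability outcome without a cut-off.

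Under Methods & Procedures, the MUC arm gets the same app, except that "the PMR component will be blocked on the version of the app that the MUC subject receives".

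The number randomised is given in two ways. Aim 1 says "We will recruit and randomize subjects (N=400". The sample size text under Study Design assigns 90 subjects to Phase 2, and Methods & Procedures describes Phase 2 as the two-arm randomised phase and Phase 1 as single-arm.

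No maximum attrition, minimum diary completion, equivalence margin, test or interval is stated for the diary comparison.

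**The concern.** A between-arm contrast isolates what differs between the arms. Here that is PMR and its introductory session, not the diary. A burdensome diary would tend to push people out of both arms alike, and the contrast would stay near zero. The reminders after three days without an entry and the payment per day of data also apply to both arms, so they do not help to separate a good diary from a poor one.

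At stake is one Aim 1 conclusion: whether the diary can be carried into a larger trial. If that rests on similar attrition, it does not follow from the data. If it rests on the questionnaire, it rests on a score that mixes opinion of the diary with opinion of relaxation. If it rests on both, the reader is not told how they are weighed.

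**Working it through.** **The plan's own figures.** None concerns diary attrition. The nearest two reproduce:
- MIDAS change, difference 5.75, SD 7, 23 per group, two-sided 0.05. SE = 7 × √(2/23) = 2.064; 5.75/2.064 − 1.96 = 0.826; power 79.5% by the normal approximation (77.8% by noncentral t), against 80% stated.
- PMR adherence, 21 of 30 (70%): exact 95% lower limit 50.6%, above 50% as stated.

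**Step 1: can the contrast tell a good diary from a poor one?** The plan names no test, so assume a pooled two-proportion z-test at two-sided 0.05, 45 per arm and the same true attrition in both arms. Exact enumeration gives the chance of a non-significant difference:
- attrition 15%: 94.5%
- attrition 50%: 95.5%
- attrition 80%: 94.6%

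At 200 per arm it is 94.9% at all three rates. The result does not depend on how bad attrition is.

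**Step 2: does the 9-item score fill the gap?** With mean D on the five diary items and R on the four relaxation items, the score is (5D + 4R)/9.
- RELAX, D = 3.2 and R = 5: (16 + 20)/9 = 4.0. The criterion is met although the diary items average well below 4.
- MUC cannot use the relaxation component. If those items are left out, the score is D alone, a different quantity from the RELAX score. If they were scored 0, the maximum would be 25/9 = 2.8 and 4 could not be reached. The plan does not say which applies.
- The plan counts drop-outs as non-compliant for PMR adherence, but gives no rule for drop-outs who return no questionnaire. If they are left out, the mean describes those who stayed.

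**Step 3: how precisely is the attrition difference estimated?** Half-width = 1.96 × √(2p(1 − p)/n), assuming 1:1 allocation. The rates are scenarios: 15% mirrors the roughly 85% diary adherence cited from the epilepsy study, 25% is the dropout assumed for the MIDAS calculation, and 50% is an upper scenario.

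| Attrition p | 45 per arm (N=90) | 200 per arm (N=400) |
|---|---|---|
| 15% | ±14.8 points | ±7.0 points |
| 25% | ±17.9 points | ±8.5 points |
| 50% | ±20.7 points | ±9.8 points |

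With 45 per arm, power to detect 40% against 60% attrition is Φ[(0.20 − 1.96 × √(2 × 0.25/45)) / √((0.24 + 0.24)/45)] = Φ[(0.20 − 0.2066)/0.1033] = 47%.

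**Step 4: could equivalence be shown?** The documents give no margin, so 10, 15 and 20 points are assumed. Power of two one-sided tests at 0.05 with a true difference of zero is 2Φ(m/SE − 1.645) − 1, set to 0 if negative. At 50% attrition:
- 45 per arm (SE 0.105): 0%, 0% and 20%
- 200 per arm (SE 0.050): 28%, 83% and 98%

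**The case against.** The strongest reply is that Aim 1 defines acceptability by a fixed score, in the sentence straight after the hypothesis. A reader might infer from the attrition sentence that equally poor attrition would cause the diary to be declared acceptable. The documents do not support that: if the score must also reach 4, equal attrition alone would not be enough. This reply stands. It limits the point to what the attrition comparison can show and to how far the score makes up for it.

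Other parts of the reply also have force:
- The no-difference hypothesis may refer to the questionnaire score rather than to attrition. The wording allows both readings. Under the first, the comparison is between scores that MUC and RELAX subjects cannot answer on the same footing.
- No test or significance level is given for this comparison, so the plan does not say that non-significance will be taken as proof. The caution is preventive.
- The remark that "only about half of the participants have full follow-through" might be read as 50% attrition. It stands in the sample size rationale and does not say that half left the study or stopped the diary. The 50% rate above is only a scenario.
- A reader might infer that the sample can never support similarity. That depends on the N and the margin: with 400 randomised, equivalence within 15 points is feasible.
- Differential attrition is worth examining, because it shows whether PMR changes diary drop-out. Retention and days of diary entry are already collected.

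What remains is that no absolute limit is set for retention or completion, the score is not specific to the diary, no rule combines the two, and no margin is given.

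**Conclusion.** The point holds in limited form. The attrition contrast cannot speak to the acceptability of a diary that both arms use, at any sample size. The mean of at least 4 is a partial safeguard, because four of its nine items concern a component blocked in MUC.

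The precision argument is conditional. With 90 randomised and 1:1 allocation, an interval of about ±15 to ±21 points means that a non-significant result would not establish similarity. With 400 it narrows to about ±7 to ±10 points. The description of Phase 2 favours 90, but the documents contradict each other. The attrition rates and margins are assumptions.

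The consequence is confined to the diary conclusion in Aim 1. The Aim 2 outcomes and the PMR adherence benchmark are not affected.

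**What to change.** - Judge the diary in absolute terms: the mean of the five diary items (at least 4) scored separately in both arms, the proportion retained, and the percentage of diary days completed. Give each a 95% CI and a threshold fixed in advance, and say whether the estimate or its lower limit must clear it. The plan already has this form for PMR adherence (70% expected, refinement below 50%).
- Keep the four relaxation items as a RELAX-only score.
- State how satisfaction, retention and completion combine, and how drop-outs without a questionnaire are handled.
- Report the between-arm attrition difference with its 95% CI as descriptive, and do not infer no difference from non-significance. If similarity is to be claimed, pre-specify a margin.
- Reconcile the randomised N (400 against 90).

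The cost is a few sentences in Aim 1 and the Analysis Plan; no new data are needed. Pooling the arms also helps precision: 45 of 90 retained has an exact 95% CI of 39.3% to 60.7%, about ±11 points, against ±20.7 for the between-arm difference. The downside is that diary acceptability becomes somewhat harder to claim.

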- 1. Please remember to use the app.
- 2. Hi, The RELAXaHEAD team is trying to reach you. Please call xxx-yyy-zzz [study phone number]?
- 3. You are due for your follow-up call/email. Please be sure to call us at xx-yyy-zzzz or respond to the email. The RELAXaHEAD team.

- 4. Remember-relaxation is beneficial for your health.
- 5. The best way to add relaxation into your routine is to pair it with an activity you do each day. Let us know if you want to discuss how to improve your adherence with the RELAXaHEAD app.
- 6. Research has suggested that the more one is able to practice relaxation, the better one's health. Log into the RELAXaHEAD app when able.
 - 7. We will text participants once a week from our NYU MCIT study phone confirming that we have recorded that they have spent x amount of time practicing PMR within the application, and asking if they have practiced PMR independently without the application that week.

Follow-up will be assured by testing the subject's phone number in front of the subject and asking for alternative contact information. Subjects will also be called/emailed.texted after 3 days of no daily diary entry. If they are not reached, an email via [contact] will also be sent as a reminder to input the data. During the calls, a designated study team member will reiterate the importance of adherence with the app. At 1,2 and 3 months, subjects will be asked to complete the MSQv2 and the MIDAS via phone or email to assess the treatment benefits. A designated study member will call the patient if they do not complete the assessment electronically. Throughout the study, subjects will be asked to record electronically any new and/or discontinued medications and interactions with the medical community. The study team also wants to collect additional patient information such as medications used before and after the research study (especially opioids), healthcare utilization, and comorbid diagnoses via i2b2, a member-driven non-profit foundation developing an open-source / open-data informatics community.

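### Aim 2 is worded as a within-group, RELAX-arm analysis, but the sample size assumes a between-arm test, no between-arm model is specified, and the Pain row adjusts for PMR adherence

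*Combined protocol and SAP*

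**What the plan says.** **Aim 2 (Purpose of the Study).** The aim reads "Aim 2: Conduct within group analyses of the RELAX approach vs MUC". Its hypothesis is about one arm over time: "We hypothesize that at 3 months compared with baseline there will be trends in the RELAX arm towards decreased disability". No RELAX-minus-MUC contrast is hypothesised.

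**Sample size (Study Design, Phase 2 text).** The size is justified first on PMR compliance. The text then adds: "The planned sample size also provided adequate power for the primary exploratory outcome", meaning change in MIDAS from baseline to 3 months. With SD 7 and about 23 evaluable patients per group, the groups are said to "achieve 80% power to detect a clinically significant difference of 5.75 between the groups", "assuming a significance level of 0.05 using a two-sided two-sample t-test".

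**Analysis Plan and Table 2.** The Analysis Plan states "Our primary outcome will be the change in the MSQv2", while Table 2 gives the 3-month change in MIDAS as the primary outcome; Aim 2 names both instruments. Neither place gives a between-arm test or model, covariates, analysis population or missing-data method for Aim 2. The Pain row of Table 2 adds that adherence to PMR will be controlled for, without saying in which model. Methods & Procedures states that the relaxation component is disabled in the MUC version of the app.

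**The concern.** An analyst following Aim 2 would test RELAX against its own baseline. An analyst following the sample-size text would compare RELAX with MUC. These are different questions, and only the second uses the randomisation.

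The difference matters because both arms may improve with no RELAX effect. Entry requires a MIDAS score above 5 and at least 4 headache days a month, so some regression to the mean is plausible. Both arms also receive the diary, written education, follow-up contacts and usual care. A pre-post change in RELAX contains all of this. Aim 2 is exploratory, but a larger trial would build on its estimate.

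The Pain-row adjustment is a separate problem. In a RELAX-versus-MUC model, PMR adherence is a post-randomisation variable, is zero by design in MUC as far as the app records it, and is part of how RELAX would work. Conditioning on it means the arm coefficient no longer estimates the randomised effect.

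**Working it through.** **Inputs from the sample-size text:** SD of change in MIDAS 7 (stated range 5 to 7); about 23 evaluable per arm; difference 5.75; two-sided alpha 0.05; stated power 80%. **Assumed, because the documents give no expected change in MUC:** a shared improvement m of 1 to 5 points in both arms, with no RELAX effect.

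**1. Which test does the stated 80% belong to?**

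- Between arms, the noncentrality is 5.75 / (7 × √(2/23)) = 2.79. With 44 df and critical value 2.015, the exact t power is 77.8%. The normal approximation gives 79.5%, which matches the stated 80%.
- Within RELAX, the noncentrality is 5.75 / (7/√23) = 3.94. With 22 df and critical value 2.074, power is 96.4%.

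The stated figure reproduces only as a between-group test.

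**2. Chance of a significant RELAX pre-post change when RELAX has no effect.** One-sample t on change, n = 23, noncentrality m√23 / SD, two-sided 0.05:

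| Shared improvement m (points) | SD 7 | SD 5 |
|---|---|---|
| 1 | 10% | 15% |
| 2 | 26% | 45% |
| 3 | 50% | 79% |
| 4 | 75% | 96% |
| 5 | 91% | >99% |

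Example: m = 3 and SD 7 give 3 × √23 / 7 = 2.06, and power 50%. The two-sample test stays at 5% in every row, because the shared improvement cancels.

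Comparing the two within-arm results does not repair this. With p the SD 7 figure, RELAX significant and MUC not occurs with probability p(1 − p): 19%, 25% and 19% for m = 2, 3 and 4.

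**3. Does the between-arm analysis need a larger trial?** With 90 randomised (1:1 assumed) and about half followed through, as the protocol now expects, 45 × 0.5 = 22.5 per arm are evaluable. The two-sample t power for 5.75 is 75.9% at 22 and 77.8% at 23 per arm. This is close to the plan's own basis.

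**4. Effect of adjusting for baseline.** With equal variances at baseline and follow-up, and correlation r, the variance of the ANCOVA estimate relative to the change-score estimate is (1 − r²) / [2(1 − r)] = (1 + r)/2. With the SD of change held at 7, 23 per arm and 43 df:

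| Assumed r | Variance ratio | Power for 5.75 |
|---|---|---|
| 0.3 | 0.65 | 92% |
| 0.5 | 0.75 | 88% |
| 0.7 | 0.85 | 84% |

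**5. Pain row.** No arithmetic applies. The covariate depends on assignment, so in a two-arm model it partly stands in for the arm indicator. Table 2 does not say which model is meant, and no numerical bias is claimed.

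**The case against.** The strongest reply is that the aim sentence itself mentions MUC, the sample-size text names a two-sample t-test on the same change score as Table 2, and Aim 2 is exploratory in a feasibility trial whose size rests first on adherence. On that reading a between-arm comparison was always intended. The documents plan no pre-post significance test and speak only of trends, so the percentages in the first table illustrate a principle and do not measure this trial's error rate. Much of this is fair: the aim sentence is inconsistent with itself, a between-arm test can be inferred, and the table depends on an assumed shared improvement. But the inferred test stands only as a sample-size assumption, the sole hypothesis is one-armed, and the Analysis Plan settles nothing. Exploratory status limits the strength of the claim; it does not turn a one-arm change into a treatment effect.

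On the Pain row, adjusting for adherence would be harmless within RELAX, and MUC participants might practise relaxation outside the app. A weekly text does ask about practice without the app, though it reads as a RELAX-arm message because it reports time recorded in the app. Neither point makes adherence a valid covariate in a between-arm comparison.

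It is also true that ANCOVA goes beyond what consistency requires. The two-sample test would remove the contradiction. The ANCOVA gain rests on assumed correlations and on normal theory, and it shrinks as the correlation rises: at r = 0.9 power is about 80%.

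**Conclusion.** The concern holds and should be fixed. The plan gives incompatible accounts of the Aim 2 analysis, and the one in the aim itself would attribute shared improvement to RELAX although a randomised comparator exists. At SD 7 and 23 per arm, the chance of a falsely attributed significant change runs from 10% to 91% for an assumed shared improvement of 1 to 5 points, and from 15% to above 99% at SD 5, against 5% for the between-arm test. The contradiction is certain from the text; the size depends on the assumed shared improvement and on a pre-post test being used. The sample size is not in question here, and Aim 1 is unaffected. The adherence adjustment is wrong in any between-arm pain model; whether one was intended is not stated.

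**What to change.** 1. Reword Aim 2 so that its main analysis is the RELAX-minus-MUC difference at 3 months in MIDAS and in MSQv2 (both are called primary), among all randomised, by ANCOVA on the baseline score with a 95% confidence interval, labelled exploratory. State this in the Analysis Plan, with the handling of missing 3-month scores.
2. Report within-arm changes descriptively only.
3. Remove PMR adherence from the between-arm pain analysis. If a dose-response question is of interest, examine it within RELAX only, as exploratory.
4. If interim scores are used for missing data ("At 1,2 and 3 months, subjects will be asked to complete the MSQv2 and the MIDAS"), allow for the fact that MIDAS "measures disability over the past 3 months": the 1-month score covers about 2 pre-baseline months (3 − 1) and the 2-month score about 1 (3 − 2).

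The cost is analysis-plan wording. Baseline and follow-up MIDAS and MSQv2 are already collected, and no extra patients are needed relative to the plan's own power basis. Under the assumptions shown, baseline adjustment raises power above the unadjusted 78%.

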The total N will be 490. We had an initial approval for N=402. Going forward, we are hoping to recruit an additional 90 subjects from the FGP Urgent Care Center and from the Neurology Urgent Care Center.

The initial stats were calculated as follows:

Sample size: Phase 1: 432 subjects, Phase 2: 90 subjects

Phase 1: The NCCIH uses the Kramer reference for power calculation. As indicated by Kraemer and colleagues, our pilot sample size (402) is based on the pragmatics of recruitment and the requisites for examining feasibility. We anticipate an adherence rate of at least 70%. If the adherence rate is below 50%, we will consider the approach in need of further refinement. Thirty patients per arm will allow estimation of an exact 95% confidence interval whose lower bound exceeds 50%. Therefore, insufficient adherence would be ruled out, assuming the true adherence rate is 70% or greater. This approach obviates the need to handle missing data, because subjects who drop out will be assumed non-compliant.

Thus, we plan to try to enroll migraine patients from the general neurology group, the NYU Headache specialists within the main academic center ([name]/ACC), the NYU Headache Center in the Men's Health Center and from [name] office. We would also like to recruit at MS Society events and other neurology events.

Research assistants will evaluate which patients are eligible to participate based on the inclusion and exclusion criteria stated below.

Phase 2: We arrived at the 90 urgent care subjects based on our initial power analysis and then the NIH's request in the Just in Time to increase the N up to 85.

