Box 1: Inclusion Criteria: Age 18-80 years (age 18-65 in urgent care); Meets migraine criteria based on the International Classification of Headache Disorders (ICHD) criteria; Migraine Disability Assessment (MIDAS) score >5.4+ headache days a month.OR Meets Chronic PTH criteria based on International Classification of Headache Disorders (ICHD) criteria, is 3-12 months post-injury, and there are 4+ headache days a month. Scoring > or = 15 on the ISI. Exclusion Criteria: Patients who have had Cognitive Behavioral Therapy, Biofeedback, or other Relaxation Therapy in the past year; Cognitive deficit or other physical problem with the potential to interfere with behavioral therapy; Alcohol or other substance abuse as determined by self-report or prior documentation in the medical record: Opioid or barbiturate use 10+ days a month; Unable or unwilling to follow a treatment program that relies on written and audio file materials; Not

having a smartphone.

Meets Insomnia criteria based on the Insomnia Severity Index (score > or = 15)

Exclusion Criteria [Box1]

Patients who have had Cognitive Behavioral Therapy,

Biofeedback or other Relaxation Therapy in the past year; Cognitive deficit or other physical problem with the potential to interfere with behavioral therapy; Alcohol or other substance abuse as determined by self-report or prior documentation in the medical record; Opioid or barbiturate use 10+ days a month; Unable or unwilling to follow a treatment program that relies on written and audio recorded materials; Not having a smartphone

VulnerableSubjects

N/A

Methods & Procedures

[Please note that Phase 1 is now complete-we are now in Phase 2 of the study]

For phase 1 of the study, a single arm study was done to assess the feasibility and acceptability of the recruitment process and the app. The duration of this Phase was 6 months. The subjects were asked to use the application for at least 3 months. Compliance was checked during this time and compliance calls were done to remind the subject to use the application. In the latter 3 months we studied if the subjects continued to use the application on their own.

July 2020: We are reopening the Phase 1 single arm study to assess the feasibility of virtual subject enrollment prior to expansion to a larger study. Phase 1 will be conducted as above with a N=30 subjects. The steps will

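### Thirty patients per arm do not rule out adherence below 50% at a true rate of 70%: the exact 95% lower bound clears 50% only 59% of the time

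*Combined protocol and SAP*

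**What the plan says.** The passage is in Study Design, in the sample-size text for Phase 1. It anticipates adherence of at least 70% and sets a threshold for concern: "If the adherence rate is below 50%, we will consider the approach in need of further refinement". It then gives the precision argument, "Thirty patients per arm will allow estimation of an exact 95% confidence interval whose lower bound exceeds 50" percent, and draws the conclusion: "Therefore, insufficient adherence would be ruled out, assuming the true adherence rate is 70% or greater". No probability is attached to that conclusion. Dropouts are counted as non-compliant, so the denominator stays at the number enrolled.

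Three other statements fix the scope:

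- The same paragraph says that "our pilot sample size (402) is based on the pragmatics of recruitment and the requisites for examining feasibility". Thirty per arm is therefore not the size of the whole pilot.
- The Phase 2 text says "Our initial sample size was justified based on the feasibility outcome of compliance with PMR among patients in the RELAX group", and continues "We anticipated an initial compliance rate of at least 75" percent. It does not repeat the claim that low adherence is ruled out.
- Methods & Procedures reopens the single-arm Phase 1 in July 2020: "Phase 1 will be conducted as above with a N=30 subjects". No adherence claim of its own is attached to that group.

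**The concern.** The precision sentence and the conclusion concern different quantities. A confidence limit is computed from the observed proportion. The conclusion is conditioned on the true proportion, and the observed proportion varies around that. If the smallest observed result that clears 50% lies at or near the anticipated rate, then a true rate equal to the anticipated one will give a failing result in a large share of samples. The sentence presents a fairly uncertain outcome as settled.

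Adherence is an Aim 1 feasibility outcome with a 70% hypothesis, and this is the only quantitative support for it in the Phase 1 text. A reader who takes thirty as sufficient could be misled in two ways: by planning a later group of that size on the same assurance, or by treating a lower limit below 50% as strong evidence against the approach when it would be common at the anticipated rate.

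**Working it through.** **Inputs.** From the Phase 1 sample-size text: n = 30 per arm; an "exact 95% confidence interval whose lower bound exceeds 50" percent; threshold 50%; true rate 70% or greater; dropouts counted as non-adherent. From the Phase 2 text: an anticipated rate of 75%. The plan does not say whether the limit is one- or two-sided. I take the usual two-sided Clopper-Pearson interval and show the one-sided version as a variant.

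**Step 1: reproduce the plan's figure.** For x adherers out of n, the two-sided exact 95% lower limit is the 0.025 quantile of a Beta(x, n − x + 1) distribution.

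| Observed | Lower limit | Above 50%? |
|---|---|---|
| 20/30 (66.7%) | 47.2% | no |
| 21/30 (70.0%) | 50.6% | yes |

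The plan's precision statement reproduces for an observed rate of 70%. The cut-off is 21 of 30, exactly the anticipated rate. Wilson and mid-P intervals give the same cut-off.

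**Step 2: probability of reaching the cut-off at a given true rate p.** P(X ≥ 21) = Σ over k = 21 to 30 of C(30, k) p^k (1 − p)^(30 − k).

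| True rate p | P(X ≥ 21) | Chance of failing to clear 50% |
|---|---|---|
| 70% | 58.9% | 41.1% |
| 75% | 80.3% | 19.7% |
| 80% | 93.9% | 6.1% |

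For a 90% chance with n = 30, the true rate would have to be 78.2%.

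**Step 3: one-sided variant.** With a one-sided 95% exact limit (0.05 quantile), 19/30 gives 46.7% and 20/30 gives 50.06%, so 20 are needed. P(X ≥ 20) at a true 70% is 73.0%.

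**Step 4: other group sizes, two-sided limit.** The plan does not state how many of the 402 use PMR or the allocation of the 90, so the group sizes marked below are assumptions.

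| Group size | Adherers needed | Lower limits either side of the cut-off | Probability at true 70% |
|---|---|---|---|
| 30 | 21 | 47.2% / 50.6% | 58.9% |
| 45 (assumes equal allocation of 90) | 30 | 48.8% / 51.0% | 74.6% (92.5% at true 75%) |
| 200 (assumes about half of 402) | 115 | 49.8% / 50.3% | 99.99% |
| 402 (assumes all use PMR) | 222 | 49.97% / 50.2% | above 99.99% |

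At a true 70%, each group size from 54 to 200 gives at least 80% probability, and each from 70 to 200 gives at least 90%. The probability moves in a saw-tooth with n because the cut-off is a whole number, so these are the sizes from which the level holds throughout the range scanned.

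**The case against.** The strongest case on the other side is about consequence.

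- **Nothing now turns on the sentence.** The text is introduced as the initial calculation, and Methods & Procedures says Phase 1 is complete. Rewording changes no enrolment, analysis or decision rule. This stands, and it limits the importance of the point.
- **Thirty was not the pilot size.** At 402, or at an assumed 200 using PMR, the assurance is true for practical purposes. This also stands. But the sentence draws its conclusion from thirty per arm, and for that number it is false.
- **The one actual group of thirty carries no such claim.** The reopened Phase 1 is there to test virtual enrolment. This is correct; that group only shows that the plan does use this size.
- **Precision convention.** Sample sizes are often justified by the interval expected if the anticipated rate is observed, and the word true may be loose usage for that. On this reading no printed figure is wrong, and indeed the interval reproduces. But the text does condition on the true rate and draws an unqualified conclusion from it, and a reader cannot be expected to substitute observed.
- **59% is the edge of the claim.** The condition is 70% or greater, and the chance rises to 80.3% at 75%. That is fair. An assurance stated for the whole range must still hold at its lower end, and even the one-sided reading gives only 73.0% there.
- **Phase 2 does not rest on it.** Its text sets no 50% limit, and the 45 per arm is an assumption. The Phase 2 figure is therefore useful information rather than a correction.

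**Conclusion.** The concern holds. Thirty patients give a lower limit above 50% when at least 21 are observed to adhere. At a true rate of 70% that happens with probability 58.9%, so the plan's unqualified conclusion is wrong for the size it names. The result rests on the two-sided exact interval and on adherence being independent between patients with a common rate. The one-sided reading gives 73.0% and does not rescue the sentence.

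The scope is narrow. The error is in the stated assurance for groups of about thirty. It does not undermine the 402-subject pilot, does not make the below-50% refinement trigger wrong, and is not repeated in the Phase 2 justification. It should be corrected because it states a design property that the stated size does not have, and because the correction is simple.

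**What to change.** Replace the concluding sentence of the Phase 1 precision argument with:

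> With 30 patients using PMR, the exact two-sided 95% lower bound exceeds 50% if at least 21 adhere; the probability of this is 59% if the true rate is 70% and 80% if it is 75%.

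Two additions would help but are not needed to correct the error:

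- For the full pilot, give the matching figure once the number using PMR is stated. For about 200, at least 115 must adhere, with probability above 99.9% at a true 70%.
- For Phase 2, give the matching figure for the actual RELAX arm. If it is 45, at least 30 must adhere, with probability 75% at a true 70% and 92% at 75%.

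The cost is an edit to the sample-size text. No extra patients are required, and the only drawback is a less favourable stated assurance for a group of thirty.
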